3.6 RANDOMIZATION

Participants will be randomized at a 1:1 ratio between the AAT and PTM treatment arms using permuted blocks of random sizes. Randomization will be stratified by treatment center. Randomization will be conducted in the Suvoda IRT system after enrollment has been completed in Advantage eClinical.

4 SAMPLE SIZE AND POWER CONSIDERATIONS

4.1 HISTORICAL DATA

The high risk acute GVHD patients included in the study population include patients with Minnesota (MN) high risk classification per the Refined Minnesota criteria, MN standard risk patients with isolated stage 2 involvement of the lower GI tract or stage 1 lower GI tract disease with skin involvement. To determine the appropriate sample size for this study, historical data were used to determine the Day 28 overall response rate expected in this population under CS treatment. In developing the Refined Minnesota risk criteria, Macmillan et al. 2015 used acute GVHD data collected from 1723 patients across multiple centers to estimate GVHD response rates in their acute GVHD risk classification of Minnesota (MN) high vs. standard risk. Among MN high risk patients in this cohort, the Day 28 overall response rate was 43% (Figure 1).

Additionally, data from patients presenting with lower GI acute GVHD in the BMT CTN 0302 and 0802 acute GVHD treatment trials and at MD Anderson Cancer Center during 2009-2012 were examined. Among these patients, those with isolated stage 2 lower GI or stage 1 lower GI and skin involvement had observed Day 28 overall response rates of 50-57% (highlighted rows in Table 3), indicating a similar level of risk as to the MN high risk category despite being classified as “standard risk” per these criteria. Therefore, they are included in the study population to increase the set of study eligible patients that may benefit from AAT+CS treatment. As a whole, these historical control data suggest a Day 28 overall response rate of approximately 50% for the study population.

Figure 1: Comparison of Day 28 Overall Response (CR+PR) Rates in MN Standard vs. High Risk acute GVHD patients (Macmillan et al. 2015).

[figure not shown]

Table 3: Observed Day 28 Response Rates for Patients with Lower GI GVHD from BMT CTN 0302/0802 Trials and MD Anderson Cancer Center

Organ Involvement	MD Anderson Cancer Center		BMT CTN 0302/0802 Trials	
	N	Day 28 CR/PR Rate	N	Day 28 CR/PR Rate
Isolated Lower GI:				
Stage 1	37	73%	8	75%
Stage 2	14	50%	9	56%
Stage 3-4	23	48%	15	67%
Lower GI + any liver:				
Stage 1	9	56%	7	43%
Stage 2	5	40%	8	50%
Stage 3-4	12	17%	5	0%
Lower GI + any skin:				
Stage 1	19	53%	30	57%
Stage 2	10	50%	17	41%
Stage 3-4	17	35%	17	41%

* Highlighted rows show Minnesota standard risk subgroups that were selected for inclusion in BMT CTN 1705 based in similar observed CR/PR rates to Minnesota high risk patients

4.2 STATISTICAL DESIGN AND SAMPLE SIZE DETERMINATION

The primary hypothesis is that the odds ratio for the overall response (CR+PR) at Day 28 between the treatment groups, adjusted for treatment center and GVHD risk (MN high vs. standard risk), is greater than 1 (AAT+CS versus PTM+CS). The primary analysis will be based on a Wald test from a logistic mixed model with the overall response as the outcomes, testing the odds ratio of treatment assignment, as described in section 6.4.1.1. The required sample size for this study is approximated using a two-sample Z-test of the difference in response rates. Historical control data indicate that the overall response rate at Day 28 for high risk acute GVHD is approximately 50%. We anticipate that AAT+CS treatment will increase the Day 28 overall response rate to 75%, corresponding to a 25% effect size. To perform a one-sided test of the superiority of AAT+CS over PTM+CS with one interim analysis for futility, we use a two-stage design with one interim analysis for futility based on a Gamma family error spending function with $\gamma = -8$. The interim futility analysis was chosen to occur after 76 patients are evaluable for Day 28 response, at a 56% information fraction. This design specification and the two-sample Z-test sample size calculation imply that a sample size of 136 patients (68 per arm) is required to sufficiently maintain a one-sided type I error of 2.5% while providing 86% statistical power for a one-sided test to detect a 25% effect size.

Operating characteristics of this sequential design with a two-sample Z-test of response rates are shown in Table 4 as an approximation to the operating characteristics provided by a logistic mixed model in this setting. Kahan and Morris 2012 demonstrated that a stratified analysis improves statistical power for a specific set of analysis techniques. Based on their findings, we expect that the power provided by an unadjusted analysis via a two-sample Z-test comparing proportions is a lower bound to the power provided by the specified logistic mixed model.

Table 4: Group Sequential Design Stopping Thresholds for Z-test of Proportions with One-Sided Type I Error 2.5%, Power 86% and an Effect Size of 25%

Info. Fraction	Sample Size	Nominal Cumulative Type II Error Rate	Futility Boundary Scales			Probability of Stopping Early for Futility	
			Difference in Proportions	Z-Statistic	Conditional Power at Alternative	Under Null	Under Alternative
0.56	76	0.004	-0.034	-0.31	0.089	0.378	0.004
1.00	136	0.139	0.163	1.96	-	-	-

4.3 SIMULATION STUDY

A simulation study was conducted to evaluate the power provided by a logistic mixed model in this sequential design. Randomized treatment assignments were generated for each simulated trial using stratified randomized block design at a 1:1 ratio with permuted blocks of size 6, with center accrual numbers obtained from those observed in participating centers of the BMT CTN 1501 study. Centers with fewer than 10 patients were combined, resulting in 6 center-groups of size 23, 19, 17, 15, 14, and 48. We assumed these groups' random effects are a random sample from a zero-mean normal distribution. Additionally, we estimated that 65% of the patients would be classified as Refined Minnesota high risk, with GVHD risk (MN high vs. standard) included as a fixed effect in the logistic model for all simulations. We considered possible effect sizes of 10%, 15%, 20%, and 25% and standard deviations for the random effects of 0.05, 0.60, and 1.00, with 1000 replicated trials simulated for each scenario.

Simulation results in Table 5 indicate that, in the near absence of a random effect (i.e., when the standard deviation of the random effect is close to zero), the statistical power is at least 94.2% to detect an odds ratio of 3.0, corresponding to an effect size of 25%. Further, when the random effect is present (standard deviation of 0.6 or 1.0), statistical power is at least 92% and 90% to detect an odds ratio of 3.0. For any other given effect size, the power levels are similar regardless of the variability of the random effects. These results support the ability of the logistic mixed model to provide at least 86% power in this group sequential design.

Table 5: Empirical Power for Logistic Mixed Model (1000 simulations per scenario)

Effect Size (AAT vs. PTM)		Power (%)		
		Standard Deviation of Random Effects		
Difference in Day 28 CR/PR		Odds Ratio	0.05	0.60
10%		1.500	25.5	24.2
15%		1.857	53.8	51.3
20%		2.500	85.0	83.4
25%		3.000	94.2	92.9
				90.1

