5.3.2.1 Stratified Mixed Effects Logistic Simulation

We simulated a stratified randomized block design using blocks of size 6, based on the distribution of patients observed in each center of the BMT CTN 1501 study. Centers with fewer than 10 patients were combined resulting in a total of 6 centers of size 23, 19, 17, 15, 14 and 48. We assumed these centers are a random sample from a larger population with standard deviations 0.05, 0.6 and 1.0. Additionally, we estimated that 35% of the patients will be classified as “high risk”; a covariate that we adjust for in all the simulations done

Simulation results indicate that in the absence of a random effect (i.e., when the standard deviation of the random effect is close to zero) our statistical power is at least 94.2% to detect an odds ratio of 3. Further, when the random effect is present (std. dev. of 0.6 and 1.0) statistical power is at least 92.9% and 90.1% to detect an odds ratio of 3 as shown in Table 5-3. We also obtain statistical power ranging from 20.8% to 25.5% when the odds ratio is 1.5 regardless of the variability between centers.

Table 5-3 Stratified Mixed Effects Logistic Model with 1000 Simulations of Size 136

Effect Size	Power (%)				
	Variance of Random Effects				
AAT - PTM	Odds Ratio	Coef.	0.0025	0.36	1.0
10%	1.500	0.406	25.5	24.2	20.8
15%	1.857	0.619	53.8	51.3	48.4
20%	2.500	0.916	85.0	83.4	79.6
25%	3.000	1.099	94.2	92.9	90.1

5.3.3 6 Month Analysis for Clinical Study Report

A clinical study report for potential regulatory submission will be prepared after all randomized subjects have completed at least 6 months of follow-up post-randomization. The database will be locked to support this clinical study report. Data transfer and unblinding will follow the study's Blinding Management Plan. This report will include descriptive statistics based on available data at time of the analysis as well as formal hypothesis testing / treatment comparisons for the primary Day 28 overall response rate (CR/PR) endpoint and secondary endpoints including GVHD-free

survival, proportion of response, proportion of response allowing for next-line therapy, and systemic infections.

The BMT CTN 1705 Statistical Analysis Plan (SAP) will elaborate further on the contents of the 6-month report.

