3.5 STUDY DESIGN

This study is a phase III, multicenter, double-blinded, randomized, placebo-controlled trial designed to compare AAT and CS to PTM and CS as first-line therapy for patients with high-risk acute GVHD. The targeted enrollment is 136 patients, accrued over three years from approximately 25 treatment centers with patients randomly allocated at a 1:1 ratio to treatment arms (68 patients per arm). Patients will be followed for one year following enrollment.

The primary endpoint is the overall (complete or partial) response to acute GVHD treatment at Day 28 post-randomization. Patients without a Day 28 response assessment will be considered failures. Acute GVHD will be graded and assessed for response based on Mount Sinai Acute GVHD International Consortium (MAGIC) Criteria (Harris et al. 2016).

The primary hypothesis is that the overall (CR+PR) response rate of high risk acute GVHD will be improved under treatment by AAT and CS compared to PTM and CS. Statistically, this will be evaluated by testing the null hypothesis that the odds ratio of overall response for the AAT+CS versus PTM+CS treatment arms is equal to 1 versus the alternative hypothesis that the odds ratio is greater than 1 after adjustment for the treatment center-group (see definition in Section 7.4.1) and Minnesota (MN) risk category (high vs. standard). An odds ratio greater than 1 indicates that the response rate is higher in the AAT+CS group compared with the PTM+CS group. This null hypothesis will be tested using a one-sided significance level of 2.5%.

One interim analysis for futility is included, to be performed once 76 patients become evaluable for the primary endpoint. There will be no early stopping for efficacy based on the interim analysis results.

To be eligible for this study, a patient must be experiencing an initial, clinically diagnosed presentation of acute GVHD after allogeneic transplant that requires systemic therapy with CS. Moreover, the acute GVHD must exhibit one of the following clinical features within 72 hours prior to enrollment: (A) high risk by Refined Minnesota Criteria (Macmillan et al. 2015, defined below) or (B) isolated stage 2 involvement of the lower gastrointestinal (GI) tract or stage 1 lower GI tract disease with skin involvement.

High-risk by Refined Minnesota Criteria (any one below):

- **Single organ involvement**
 - a. Stage 4 skin
 - b. Stage 3-4 lower GI
 - c. Stage 1-4 liver
- **Multiple organ involvement**

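### The mixed-model power tables (SAP Table 5, Protocol Table 5-3) overstate power for 136 patients: 94.2/92.9/90.1% at odds ratio 3 recomputes to about 86%, 82–84% and 77–79%

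*SAP*

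**What the plan says.** The primary test is a Wald test on the treatment odds ratio from a logistic mixed model with a center-group random effect and a fixed effect for Minnesota risk. On the level, SAP 3.5 says: "This null hypothesis will be tested using a one-sided significance level of 2.5"%. The sample size comes from a two-sample Z-test of 50% versus 75% with 68 per arm and 86% power. SAP 4.2 puts it this way: "We anticipate that AAT+CS treatment will increase the Day 28 overall response rate to 75%, corresponding to a 25% effect size".

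A simulation is then offered for the mixed model itself. It uses six center-groups (23, 19, 17, 15, 14 and 48 patients), stratified blocks of 6, center SDs of 0.05, 0.6 and 1.0, and 1,000 trials per scenario.

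- Protocol 5.3.2.1, near-zero center variance: "our statistical power is at least 94.2% to detect an odds ratio of 3".
- Protocol 5.3.2.1, SD 0.6 and 1.0: "statistical power is at least 92.9% and 90.1% to detect an odds ratio of 3 as shown in Table 5-3".
- SAP 4.3: "the statistical power is at least 94.2% to detect an odds ratio of 3.0, corresponding to an effect size of 25" points.
- SAP 4.3, conclusion: "These results support the ability of the logistic mixed model to provide at least 86% power in this group sequential design".

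The power figures are the same in both documents, but the risk mix is not. The protocol states "we estimated that 35% of the patients will be classified as" high risk; the SAP states "we estimated that 65% of the patients would be classified as Refined Minnesota high risk".

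**The concern.** At SD 0.05 there is almost no center effect. The mixed model should then behave like a simple two-arm comparison of the same 136 patients. Protocol Table 5-2 gives that comparison 21.24%, 41.9%, 65.2% and 85.9% power at 10, 15, 20 and 25 points. Table 5-3 gives 25.5%, 53.8%, 85.0% and 94.2%. The 15- and 25-point rows use matching odds ratios in both tables, yet they differ by about 12 and 8 points. Monte Carlo error with 1,000 trials is at most 1.6 points.

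The simulation is the only direct evidence on power for the specified primary analysis; the Z-test is presented as an approximation to it. A reader would take power at odds ratio 3 to be at least 90% whatever the center variation, and could over-read a non-significant result as evidence against an effect.

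**Working it through.** **Inputs.** From the documents: 68 per arm, one-sided 2.5%, 50% control rate, and the center-groups, block size, SDs and odds ratios (OR) listed above. The documents do not give the intercept or the risk coefficient. I assume a 50% control rate at a center effect of zero, and vary the risk odds ratio from 0.4 to 1.0 and the high-risk share between 35% and 65%.

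**Step 1: the Z-test design reproduces.** The pooled rate is 0.625. The null SE is √(2×0.625×0.375/68) = 0.0830 and the alternative SE is √((0.25+0.1875)/68) = 0.0802. Power = Φ((0.25 − 1.96×0.0830)/0.0802) = 86.2%.

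**Step 2: a ceiling without center effects.** SE(log OR) = √(1/(68×0.25) + 1/(68×0.1875)) = 0.370 and log 3 = 1.099, so approximate power is Φ(1.099/0.370 − 1.96) = 84.3%. Exact binomial enumeration of the Wald test gives:

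| OR | 50% control | Maximum, control 10–80% | Printed, SD 0.05 |
|---|---|---|---|
| 3 | 85.7% | 88.4% | 94.2% |
| 2.5 | 72.2% | 75.0% | 85.0% |
| 1.857 | 41.4% | 42.9% | 53.8% |
| 1.5 | 20.9% | 21.3% | 25.5% |

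The printed 94.2% has a Monte Carlo SE of √(0.942×0.058/1000) = 0.7 points. It lies 5.8 points above the maximum, so the unstated intercept cannot explain it.

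**Step 3: simulation of the described design.** Random-intercept logistic model, maximum likelihood by 25-node Gauss-Hermite quadrature, Wald z > 1.96, 65% high risk, risk OR 1, 5,000 trials per cell (simulation error about 0.5–0.7 points). Columns are SD 0.05 / 0.6 / 1.0.

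| OR | Printed (%) | Recomputed (%) | Excess (points) |
|---|---|---|---|
| 3 | 94.2 / 92.9 / 90.1 | 85.7 / 83.6 / 79.1 | 8.5 / 9.3 / 11.0 |
| 2.5 | 85.0 / 83.4 / 79.6 | 72.7 / 70.2 / 65.2 | 12.3 / 13.2 / 14.4 |
| 1.857 | 53.8 / 51.3 / 48.4 | 43.1 / 40.7 / 34.9 | 10.7 / 10.6 / 13.5 |
| 1.5 | 25.5 / 24.2 / 20.8 | 21.9 / 19.0 / 18.4 | 3.6 / 5.2 / 2.4 |

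Across the assumed risk shares and risk odds ratios, power at OR 3 is 85.5–86.2%, 81.9–83.8% and 77.4–79.2%. A Laplace fit with 10,000 trials (risk OR 1) gives 85.9%, 82.8% and 78.7%.

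**Step 4: conditional or marginal effect.** The SAP equates OR 3 with 25 points. The odds ratio in a random-intercept model is conditional on center. Averaging expit(log 3 + center effect) over the center distribution gives an AAT rate of 73.5% at SD 0.6 and 71.4% at SD 1.0, not 75%. Holding 50% versus 75% marginally needs OR 3.27 and 3.72, and power is then 88.0% and 90.3%. At SD 0.05 the two readings coincide.

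**Step 5: the 20-point row.** 50% versus 70% gives (0.7/0.3)/(0.5/0.5) = 2.333; the tables print 2.500. At 2.333 power is 66.5%, 62.3% and 59.3%.

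**Step 6: possible explanations.** One-sided 5% with 50% control gives 91.7%, 90.3% and 86.9% at OR 3, below print, but 32.5% at OR 1.5 and SD 0.05, above the printed 25.5%. The likelihood-ratio test adds at most about 1.6 points at OR 3. Fixed center effects at OR 3 reach only 87–88%, 84–85% and 80–81%. At one-sided 2.5% the printed levels need roughly 180–190 patients: 191 patients (risk log OR −0.6, 4,000 trials) give 95.3%, 92.9% and 90.1% at OR 3. The documents do not show whether a wrong sample size is the cause.

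**The case against.** The strongest objection is that neither simulation section states its significance level or intercept. At one-sided 5% and a control rate of about 37%, simulated power is 93.0/92.0/89.1% at OR 3 and 55.1/51.0/47.7% at OR 1.857, close to print. At OR 2.5 it is 84.0/79.5/78.2%, about 4 points low at SD 0.6. This is a live partial explanation, but OR 1.5 at SD 0.05 still gives 31.5% against 25.5% printed. If it were the cause, the tables would describe a test at twice the planned level.

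Second, the size of the gap depends on the assumed 50% control rate. That stands in part. Two simulations near 37% control at one-sided 2.5% give 88.3/85.7/80.3% and 87.0/82.5/81.7%, so the excess at OR 3 falls to about 6–7, 7–10 and 8–10 points. The documents' own control rate is 50%.

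Third, the SAP defines its scenarios by differences in response rate. On that reading the 86% conclusion is acceptable and the SD 1.0 cell at 25 points reproduces. This is right as far as it goes, but it does not rescue 94.2% at SD 0.05, and both texts state power for an odds ratio of 3.

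Fourth, 35% and 65% are complements, so this may be only a relabelled covariate. That is plausible, but the documents still need to agree.

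The description of the Z-test as a lower bound is not contradicted. On the same OR 3 data the Z-test gives 86.1/82.5/75.3% against 85.7/83.6/79.1% for the mixed model, and the SD 0.05 difference is within simulation error.

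**Conclusion.** The concern holds. At one-sided 2.5% with 136 patients and a 50% control rate, power of the mixed model at OR 3 is about 86%, 82–84% and 77–79% for center SD 0.05, 0.6 and 1.0. The printed figures are too high by 8–9, 9–11 and 11–13 points. The result rests on the assumed intercept and risk effect, but no control rate from 10% to 80% brings exact no-center power at OR 3 above 88.4%. The claim of at least 86% is borderline at SD 0.05 and unsupported at SD 0.6 and 1.0 for the listed odds ratio. It holds at those two SDs if the effect is fixed as a marginal 50% versus 75%.

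This is a wrong statement of power that should be fixed, not a design flaw. No sample size, boundary or decision rule uses these tables. The cause of the discrepancy cannot be identified from the documents.

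**What to change.** Rerun the simulation at 136 patients and one-sided 2.5%. State the level, the intercept (control rate), the risk coefficient and a single high-risk share used in both documents. Say whether each row fixes a conditional odds ratio or a marginal difference, and correct the odds ratio in the 20-point row. Replace Protocol Table 5-3 and SAP Table 5 with the new results. Restate the sentences built on them: 94.2% in both documents, 92.9% and 90.1% in the protocol, 92% and 90% in the SAP, and the SAP's closing claim of 86%. The Z-test calculation and its description as conservative or a lower bound can stay.

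The cost is one simulation run and a text correction in two documents. The stated power becomes less favourable. No patients are added, and the analysis and boundaries do not change.

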5 ANALYSIS POPULATION

5.1 INTENTION TO TREAT POPULATION

The intention-to-treat (ITT) population consists of all randomized subjects, classified according to their randomized treatment assignments. All randomized subjects are included, regardless of whether the assigned study treatment was truly administered. This population comprises the primary efficacy analysis population for the study.

5.2 MODIFIED INTENTION TO TREAT POPULATION

The modified intention-to-treat (mITT) population consists of all subjects from the intention-to-treat population who initiate their randomized treatment.

5.3 SAFETY ANALYSIS POPULATION

The safety analysis population will include all randomized subjects who received at least one dose of study treatment. Subjects will be classified according to the study treatment received. If a patient receives a dose of the incorrect study treatment (study treatment mismatched to the randomized assignment), they will be classified as follows:

- If incorrect study treatment is received for the entire treatment period, the patient will be included in the treatment group corresponding to the study treatment received.
- If incorrect study treatment is received for only one dose and the correct treatment is received for all other doses, the patient will be included in the correct treatment group with a narrative provided for any events occurring during the period for which the subject is incorrectly dosed.
- If incorrect study treatment is received for more than one dose and the correct treatment is received for at least one other dose, the patient will be included in group corresponding to the majority of received doses; if equal numbers of doses of both treatments were received, they will be classified by their randomized assignment. A narrative will be provided for any events occurring during periods for which the subject was incorrectly dosed.

5.4 PHARMACOKINETIC ANALYSIS POPULATION

The pharmacokinetic (PK) analysis population will include all subjects who received at least one dose of study treatment and with at least 1 quantifiable serum AAT antigen concentration or serum AAT concentration with functional activity. This population will be analyzed using the treatment the subject actually received.

6 ANALYSIS VARIABLES

6.1 ACUTE GVHD RESPONSE DEFINITIONS

The response of acute GVHD to study treatment is evaluated by comparing the organ staging at the assessment time to the maximum GVHD organ staging within 72 hours prior to enrollment. Organ staging is performed in the acute GVHD target organs skin, upper GI, lower GI, and liver according to MAGIC criteria (Harris et al. 2016), which are shown in Table 6.

Table 6: Acute GVHD Organ Staging per MAGIC Criteria (Harris et al. 2016)

Stage	Skin	Lower GI	Upper GI	Liver
0	No active (erythematous) GVHD rash	Adult: Diarrhea 0-499mL/day or 0-3 episodes/day Child: 0.0-9.9mL/kg/day or 0-4 episodes/day	No or intermittent nausea, vomiting, or anorexia	Bilirubin < 2.0 mg/dL
1	Maculopapular rash < 25% BSA	Adult: Diarrhea 500-999mL/day or 3-4 episodes/day Child: 10.0-19.9mL/kg/day or 4-6 episodes/day	Persistent nausea, vomiting, or anorexia	Bilirubin 2.0-3.0 mg/dL
2	Maculopapular rash 25-50% BSA	Adult: Diarrhea 1000-1500mL/day or 5-7 episodes/day Child: 20.0-30.0mL/kg/day or 7-10 episodes/day	---	Bilirubin 3.1-6.0 mg/dL
3	Maculopapular rash > 50% BSA	Adult: Diarrhea > 1500mL/day or > 7 episodes/day Child: > 30.0mL/kg/day or > 10 episodes/day	---	Bilirubin 6.1-15.0 mg/dL
4	Generalized erythroderma (> 50% BSA) plus bullous formation and desquamation > 5% BSA	Severe abdominal pain with or without ileus or grossly bloody stool (regardless of stool volume)	---	Bilirubin >15.0 mg/dL

Response Definitions:

- Complete response (CR) is defined as having a stage of 0 in all evaluable organs.
- Very good partial response (VGPR) is defined as a quantitative and functional response that closely approximates CR. Patients must have all of the following clinical features:
 - No rash or rash involving <25% of body surface area (BSA) without bullae (residual faint erythema and hyperpigmentation do not count)
 - Serum bilirubin <2mg/dl or <25% of baseline at enrollment
 - Ability to tolerate food or enteral feedings with predominantly formed stool (no overt GI bleeding or cramping and no more than occasional nausea or vomiting)
- Partial response (PR) is defined as improvement in one or more acute GVHD target organs without progression in others. Note that VGPR is a subset of PR.
- Mixed response (MR) is defined as improvement in one or more organs with deterioration in another organ manifesting acute GVHD symptoms or development of acute GVHD symptoms in a new organ.
- No response (NR) is defined as the absence of improvement or progression in any organ.
- Progression is defined as deterioration in at least one organ without any improvement in others.

Patients who die will be classified as non-responders (NR). Patients who have an escalation of prednisone-equivalent steroid dose to 2.5mg/kg/day or higher will be classified as NR with the following exception: if a patient received a prednisone-equivalent dose of 2.5mg/kg/day or more on the randomization day, maintaining this starting dose is not automatically considered an NR, but escalation to a dose higher than the starting one

is an NR; moreover, if their dose is tapered below 2.5 mg/kg/day and later re-escalated to 2.5 mg/kg/day or above, they will be classified as an NR.

The receipt of next-line GVHD therapy also may impact how a patient is classified for GVHD response. This affects the following endpoints as described:

- **Overall Response at Day 28, Duration of Response, Acute GVHD Response to AAT/PTM, Overall and Organ Specific Response Rate by GVHD and Biomarker-based risk Classifications:** If a patient receives next-line GVHD therapy prior to a GVHD assessment visit, they will be classified as a non-responder (NR) for that assessment time.
- **Acute GVHD Response Allowing for Approved Next Line Therapy:** If a patient receives next-line GVHD therapy that is not approved by the protocol chairs prior to a GVHD assessment visit, they will be classified as a non-responder (NR) for that assessment time. However, the receipt of protocol chair-approved next-line therapy has no impact on the grading of GVHD response for this endpoint.
- **GVHD-free Survival:** If a patient receives next-line GVHD therapy while being event-free, they will be classified as an event at the time point of the therapy's initiation.

6.2 PRIMARY ENDPOINT – OVERALL RESPONSE AT DAY 28

Overall response at Day 28 is defined as having a complete or partial response at Day 28, i.e. having partial or complete resolution of acute GVHD symptoms in some organ(s) without worsening in any other(s) along with being alive, free of any next-line GVHD therapy, and free of escalation of prednisone-equivalent steroid dose to 2.5mg/kg/day or more. Patients who have an escalation of prednisone-equivalent steroid dose to 2.5mg/kg/day or higher will be classified as NR with the following exception: if a patient received a prednisone-equivalent dose of 2.5mg/kg/day or more on the randomization day, maintaining this starting dose is not automatically considered an NR, but escalation to a dose higher than the starting one is an NR; moreover, if their dose is tapered below 2.5 mg/kg/day and later re-escalated to 2.5 mg/kg/day or above, they will be classified as an NR.

Organ staging is performed by MAGIC criteria, shown in Table 6. Patients with a missing Day 28 acute GVHD assessment will be classified as non-responders (NR). A Day 28 acute GVHD assessment conducted out of window (refer to Section 7.1 for visit window definition) will be considered as missing.

A supplementary analysis described in Section 7.4.3.4 will include adjustment for the refined Minnesota risk category and the MAGIC biomarker risk score (Srinagesh et al. 2019). The MAGIC biomarker risk score will be computed from baseline levels of ST2 and REG3 α per the following algorithm:

- For each patient, compute their estimated 6 month non-relapse mortality risk \hat{p} according to

$$\log(-\log(1 - \hat{p})) = -11.263 + 1.844 \log_{10} ST2 + 0.577 \log_{10} REG3\alpha$$

- If $\hat{p} < 14.1\%$, biomarker score = 1; else if $\hat{p} > 29.0\%$, biomarker score = 3; else, biomarker score = 2

